
Other Sites

No other sites

Protocol

Abstract

Hypertensive disorders of pregnancy (HDP) are stress tests which may identify women at high risk of future cardiovascular disease (CVD), the leading cause of death among women. Given the public health impact of HDP and CVD, there is a compelling need to identify scalable interventions to improve preventative care among women who have risk identified during pregnancy. We will examine the effects of delivering electronic prompts to obstetric care providers (nudge) on transitions of care in the postpartum period. We will conduct a pilot randomized trial to evaluate whether this nudge intervention will improve postpartum counseling and lead to greater follow-up with preventative care providers among women with HDP. **Objectives**

Overall objectives

The objective of the study is to evaluate the effect of a hospital-wide initiative using electronic prompts to encourage physicians to transition care for women with HDP to continuity care providers in accordance with national society guidelines.

Primary outcome variable(s)

The primary outcome measure is documentation of counseling about transitioning care to a continuity care provider (primary care or cardiology) at the postpartum visit.

Secondary outcome variable(s)

Secondary outcomes include 1. Electronic prompts opened by obstetric care providers within 1 week of receipt. 2. Documentation of CVD risk at the postpartum visit. 3. Use of scripted dot phrases (available in Epic) for counseling on transitions of care and CVD risk in the postpartum note. 4. Attendance at a primary care or cardiology visit for preventative care within 6 months of delivery.

Background

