HDP. A significant proportion of women with HDP do not see a preventative care provider (primary care, cardiology) in the months after delivery.¹⁰⁻¹² Black women are particularly vulnerable to being lost to follow-up after complicated pregnancy.^{10,11} The HSM program is an innovative, patient-centered program that monitors postpartum blood pressure remotely using a text-based interface. It is supported by the Way to Health platform. HSM improves blood pressure management in the two weeks after delivery and eliminates racial disparities in blood pressure ascertainment during that time.^{13,14} However, enrollment in HSM did not improve follow-up in the year after delivery, with less than 1/3 of women having a preventative care visit.¹⁵ Poor follow-up is likely multifactorial, but may be driven by inadequate patient counseling in the postpartum period. Among women enrolled in HSM, only 21% of women were counseled on follow-up with primary care and only 4% were counseled on CVD risk at their postpartum visits based on chart review.¹⁶ Nudges are effective for changing medical decision-making and improving clinical outcomes. Nudges utilize concepts from behavioral economics to subtly change the decision-making environment to facilitate evidence-based care and can be delivered to patients, providers, or both.¹⁷ Examples of nudges include electronic prompts to order cancer screening and electronic defaults that guide ordering practices.¹⁸ Nudges are low cost, scalable using Electronic Medical Record (EMR) systems, and improve rates of preventative services including influenza vaccination, referral to mammography, and statin prescription for CVD prevention.¹⁹⁻²²

References:

1. American College of Obstetricians and Gynecologists; Task Force on Hypertension in Pregnancy. Executive summary: hypertension in pregnancy. *Obstet Gynecol* 2013;122:1122-31.

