This study will be a randomized, controlled superiority trial to evaluate a hospital-wide initiative to improve counseling for postpartum women who experienced HDP during their pregnancy or in the immediate postpartum period. Hypotheses: 1. We hypothesize that the prompt will increase the proportion of women counseled on transitioning care to a primary care provider or cardiologist after pregnancy (primary outcome). 2. We hypothesize that the provider nudge will increase the proportion of women attending a preventative care visit within 6 months of delivery as assessed by chart review and patient surveys. The HSM daily log generated through the Way to Health platform will be used to generate lists of patients who eligible for the study. For each eligible woman, the date of and obstetric care provider for her postpartum visit will be recorded within 3 weeks of delivery. Patients will then be randomly assigned to a control group with no intervention (usual care through HSM) or the intervention group (physician nudge) using simple 1:1 randomization through the Way to Health Platform. If a woman is randomized to the intervention arm, her obstetric care provider for her postpartum visit will receive a staff message in Epic (Penn Chart) that his/her patient has an upcoming postpartum visit. The message will be sent 1 week before the scheduled visit. The message will have patient-specific information including hypertensive diagnosis, blood pressure medication(s), gestational diabetes diagnosis, and primary care provider as listed in the Epic banner. The message will also have dot phrases for recommended counseling and contact information for UPHS primary care and cardiology providers. There will be a dot phrase recommending follow-up with primary care or cardiology; counseling on risk of future CVD; and recommending aspirin in a future pregnancy. A web-based survey will be distributed to all women in the study 6 months after delivery through the Way to Health platform. The survey will assess attendance at a preventative care visit, social determinants of health, health status, and insurance status after delivery. Demographic characteristics, medical and obstetric history, hypertensive disorder, laboratory test results (platelet count, creatinine, liver function tests, urine protein, total cholesterol, triglycerides, LDL-C, HDL-C, glucose, hemoglobin A1c), blood pressure measurements, height, weight, and office visits within 6 months of delivery will be abstracted from the EMR. We will perform detailed abstraction of counseling at the postpartum visit and additional office visits within 6 months of delivery focusing on 1) health maintenance 2) hypertension, or 3) cardiovascular risk reduction. Two reviewers will assess counseling at each visit. We will obtain data on obstetric care providers including level (resident physician, attending physician, nurse practitioner, physician assistant, or certified nurse midwife), gender, and years in practice from publicly available databases or websites online.

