A flowsheet of patient participation is attached. Subjects will be identified through the HSM daily log. A waiver of informed consent is requested for the intervention portion of this study. At 30 days after discharge, all participants, regardless of study arm will receive the following message "Hello from Heart Safe Motherhood! We hope you are doing well. Dont forget to follow-up with your primary or heart doctor in the next 2-4 weeks. If you were given an appointment, make sure to keep it. If you want to make an appointment with a heart doctor focused on women's health, call [contact]. Have a great day!" At 6 months postpartum, women will receive a secure text message through the Way To Health platform. "We are trying to understand how women with high blood pressure or preeclampsia stay healthy after delivery. Respond yes if you are willing to complete a survey. You will receive \$5 for participating." If she responds yes, she will receive a survey link integrated with Way To Health. Patient information will be obtained from the electronic medical record including demographic characteristics, medical and obstetric history, hypertensive disorder, laboratory test results (platelet count, creatinine, liver function tests, urine protein, total cholesterol, triglycerides, LDL-C, HDL-C, glucose, hemoglobin A1c), blood pressure measurements, height, weight, and office visits within 6 months of delivery. We will perform detailed abstraction of counseling at the postpartum visit and additional office visits within 6 months of delivery focusing on 1) health maintenance 2) hypertension, or 3) cardiovascular risk reduction. Two reviewers will assess counseling at each visit (from the discharge summary and after visit summary). We will obtain data on obstetric care providers including level (resident physician, attending physician, nurse practitioner, physician assistant, or certified nurse midwife), gender, and years in practice from publicly available databases or websites online.

The following documents are currently attached to this item:

There are no documents attached for this item.

Deception

Does your project use deception?

No

International Research

Are you conducting research outside of the United States?

No

Analysis Plan

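### The only stated source rule for scoring counselling omits the postpartum visit note, where the plan itself expects the counselling dot phrases to appear

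*Combined protocol and SAP*

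**What the plan says.** The primary outcome (Objectives, and again in the Analysis Plan) is "documentation of counseling about transitioning care to a continuity care provider (primary care or cardiology) at the postpartum visit". Neither section limits it to a type of record.

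The records are named once, in Study Procedures, Procedures: "Two reviewers will assess counseling at each visit (from the discharge summary and after visit summary"). The Design section has the same two-reviewer sentence without a source. Subject Confidentiality names Epic and the patient surveys as data sources, but no record type.

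The third secondary outcome in the Objectives does name a record: "Use of scripted dot phrases (available in Epic) for counseling on transitions of care and CVD risk in the postpartum note". Its two topics are those of the primary outcome and of the CVD-risk outcome.

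The phrases are part of the intervention. Under Design, "If a woman is randomized to the intervention arm, her obstetric care provider for her postpartum visit will receive a staff message in Epic", and "The message will also have dot phrases for recommended counseling and contact information for UPHS primary care and cardiology providers". Their content is described there too: "There will be a dot phrase recommending follow-up with primary care or cardiology; counseling on risk of future CVD".

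The control-arm planning rate comes from the Background, where "only 21% of women were counseled on follow-up with primary care" and 4% were "counseled on CVD risk at their postpartum visits based on chart review". The types of record read in that review are not stated.

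**The concern.** The endpoint is documentation, so the list of records read is part of its definition. The one list given leaves out the document in which the plan expects the intervention's own text to appear. A provider could paste the transition-of-care phrase into the note, and the visit would then count for the dot-phrase outcome. If nothing equivalent appeared in the after visit summary, a literal reading would still score the primary outcome as absent. Having two reviewers does not help, because both would read the same restricted list.

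A lesser ambiguity is that the plan does not define a discharge summary for an outpatient visit 4-12 weeks after delivery. If it means the delivery-admission document, using it would conflict with the endpoint's limit to the postpartum visit. No bias is claimed from that, but abstractors could read the rule in different ways.

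At stake are the power of the primary comparison and the need to settle what counts as documented before anyone has seen the data.

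**Working it through.** **1. The texts side by side.**

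| Section | Record named |
|---|---|
| Primary outcome (Objectives; Analysis Plan) | none; documentation at the postpartum visit |
| Design, two-reviewer sentence | none |
| Procedures, two-reviewer sentence | discharge summary and after visit summary |
| Third secondary outcome (Objectives) | postpartum note |
| Subject Confidentiality | Epic as a system |

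No section names the note as a source for the primary outcome or the CVD-risk outcome.

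**2. The plan's own sample size.** Inputs from Accrual: 21% vs 40%, 222 randomised 1:1, 20% not attending, 80% power. From the Analysis Plan: two-sided alpha 0.05.

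- Unpooled variance: n per arm = (1.960 + 0.842)² × (0.21×0.79 + 0.40×0.60) / 0.19² = 88.25, rounded up to 89. Then 2 × 89 / 0.8 = 222.5, which matches 222.
- Pooled variance: 91 per arm, or 228 after the same inflation.
- Attenders per arm at 222: 222 × 0.8 / 2 = 88.8. Power at 88.8 is 79.0% pooled and 80.2% unpooled.

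The stated figure reproduces, and it leaves no spare power.

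**3. Illustration with equal capture.** Suppose the named records capture a share s of documented counselling in both arms. The documents give no value for s; the values below are assumptions. Observed rates are s × 0.21 and s × 0.40, so:

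- relative risk = (s × 0.40) / (s × 0.21) = 1.90 for any s
- risk difference = s × 0.19

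| s (assumed) | Rates | Risk difference | RR | Power, pooled / unpooled |
|---|---|---|---|---|
| 1.0 | 21.0% vs 40.0% | 19.0 points | 1.90 | 79.0% / 80.2% |
| 0.9 | 18.9% vs 36.0% | 17.1 points | 1.90 | 72.7% / 73.9% |
| 0.8 | 16.8% vs 32.0% | 15.2 points | 1.90 | 65.7% / 66.9% |

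This table treats 21% and 40% as full-capture rates. If they already rest on the two named records, the rule costs no planned power.

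**4. The alternative case, for the planning rate.** Suppose instead that the 21% came from the two named records and that these capture 90% or 80% of what the note plus after visit summary would show (again assumed). On the fuller list the control rate is 0.21 / 0.9 = 23.3% or 0.21 / 0.8 = 26.3%. At 222, keeping the 19-point difference gives power of 77-79% or 76-77%. Keeping the relative risk of 1.90 gives 85-86% or 91-92%. Sections 3 and 4 are alternative hypotheses, and the documents support neither over the other.

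**The case against.** The strongest reply is that the parenthesis is loose drafting. The endpoint itself has no record limit, Procedures promises detailed abstraction of the postpartum visit, and the dot-phrase outcome obliges someone to open the note. For harm to occur, the team would have to find the transition phrase there and still score counselling as undocumented. This is plausible and limits the weight of the point. It does not remove it: the Procedures sentence is a stated rule, and as written it does not list the note.

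A second reply is that note text may carry over into the after visit summary. The documents do not say either way, so the loss may be zero.

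A reader might go further and infer that the rule biases the comparison between arms, because only intervention-arm messages carry the phrases. With unequal capture the relative risk would indeed be multiplied by the ratio of the intervention-arm to the control-arm capture rate. The documents do not establish that this happens. The phrases are described as available in Epic. Randomisation is by patient, so a provider who has received a message could use them for control patients too. The scoring rule is the same in both arms. No capture rate is given for either arm, and the direction is unknown.

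Nor do the documents support saying that the primary outcome will be scored without the note, or that the rule flatly contradicts the endpoint. The after visit summary does come from the visit. This is an omission whose effect depends on a literal reading.

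**Conclusion.** The omission is certain on the text and bears on the primary outcome and the CVD-risk outcome. The dot-phrase outcome names its own source and is unaffected. Followed literally, the rule could miss counselling recorded only in the note and so make two outcomes disagree about the same visit. The consequence is unquantified: the equal-capture figures rest on assumed shares and show only how little slack there is at 222. They are not an estimate of loss, and they do not show that the sample size is wrong. The point merits correction because it concerns the primary endpoint and is cheap to settle before abstraction, not because harm has been demonstrated.

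**What to change.** Before abstraction starts:

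1. Rewrite the parenthesis in Procedures so that counselling at each visit is scored from the provider's note for that visit (for the postpartum visit, the postpartum note) and the after visit summary of the same visit. Keep the discharge summary only if it means a document of that visit, and then under its Epic name. Make the Design sentence agree.
2. State that the same list applies in both arms.
3. Find out which record types the chart review behind the 21% used. If they match the revised list, nothing else changes. If they differ, restate the planning rates and the power that 222 gives, leaving the sample size as it is.

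The cost is a short text change in the protocol and abstraction form, one enquiry about the previous chart review, and one further document per visit for the additional office visits. The postpartum visit adds no reading, because its note must already be opened for the dot-phrase outcome.

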Sample size calculations were based on the assumption that 21% of patients in usual care and 40% of patients receiving a provider nudge would have documentation about transitioning care. A sample size of 222 patients (randomized 1:1) would provide 80% power to detect this difference assuming 20% of patients will not attend their postpartum visit. Approximately 100 women are enrolled in HSM each month at Pennsylvania Hospital. We anticipate that over 90% of those women receive prenatal care at a UPHS practice (n=90 per month), and at least 80% will attend a postpartum visit (n=72). We thus anticipate that 222 women could be enrolled in 3-4 months, allowing for 6-month follow-up during the grant period.

Key inclusion criteria

1. At least 18 years old. 2. Have a diagnosis of HDP during delivery admission or have a diagnosis made at time of evaluation in the Perinatal Evaluation and Treatment Unit after discharge from the delivery admission. HDP diagnoses are based on criteria from the American College of Obstetricians and Gynecologists (ACOG). 3. Enrolled in HSM at Pennsylvania Hospital. 4. Have a postpartum visit with a UPHS provider scheduled 4-12 weeks after delivery.

Key exclusion criteria

1. Women diagnosed with chronic hypertension (CHTN) without superimposed pre-eclampsia (PEC).

Vulnerable Populations

Children Form

Pregnant women (if the study procedures may affect the condition of the pregnant woman or fetus) Form

Fetuses and/or Neonates Form

Prisoners Form

Other x None of the above populations are included in the research study

The following documents are currently attached to this item:

There are no documents attached for this item.

Populations vulnerable to undue influence or coercion

This is a hospital-wide initiative which will equally include all postpartum women in HSM who do not meet exclusion criteria.

Subject recruitment

The HSM daily log generated through the Way to Health platform will be used to generate lists of patients who eligible for the study. For each eligible woman, the date of and obstetric care provider for her postpartum visit will be recorded within 3 weeks of delivery.

Will the recruitment plan propose to use any Penn media services (communications, marketing, etc.) for outreach via social media avenues (examples include: Facebook, Twitter, blogging, texting, etc.) or does the study team plan to directly use social media to recruit for the research?

No

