We hypothesize that a provider nudge will increase the proportion of women who are counseled about 1) transitioning care and 2) CVD risk after pregnancy complicated by HDP. This is designed as a superiority trial. We hypothesize that the provider nudge will lead to improved follow-up with continuity care providers. Primary efficacy endpoint: 1. Documentation of counseling about transitioning care to a continuity care provider (primary care or cardiology) at the postpartum visit. Secondary efficacy endpoints: 1. Documentation of CVD risk at the postpartum visit. 2. Attendance at a primary care or cardiology visit for preventative care within 6 months of delivery. Chi square or Fishers exact test will be used to compare categorical data. T-test will be used to compare parametric data. Mann-Whitney U test will be used to compare non-parametric data. Univariate comparisons will be made between exposure (intervention) and outcome. Proportion and relative risk (95% CI) will be presented for primary and secondary outcomes. Multivariable logistic regression models will be created to control for potential confounders. Outcomes will be analyzed by the intention to treat principle. Our threshold for statistical significance will be two-side with alpha 0.05. Exploratory analyses: Primary and secondary outcomes will be analyzed by race (Black vs. Non-Black) based on data that HSM reduced racial disparities in blood pressure ascertainment outcomes. We will explore whether there is an interaction of race with regards to counseling and follow-up. We will also assess time trends in counseling over the study period.

The following documents are currently attached to this item:

There are no documents attached for this item.

Data confidentiality

- Paper-based records will be kept in a secure location and only be accessible to personnel involved in the study.**
- Computer-based files will only be made available to personnel involved in the study through the use of access privileges and passwords.**
- Prior to access to any study-related information, personnel will be required to sign statements agreeing to protect the security and confidentiality of identifiable information.**
- Wherever feasible, identifiers will be removed from study-related information.**

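### The Analysis Plan has no sparse-data method for adjusted and race-interaction models of CVD-risk documentation, a secondary endpoint with about 3.6 expected control events

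*Combined protocol and SAP*

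**What the plan says.** The Analysis Plan opens by hypothesising that the nudge raises counselling on both transition of care and CVD risk. It then lists "Secondary efficacy endpoints: 1. Documentation of CVD risk at the postpartum visit".

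Three analyses bear on that endpoint:

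- **Unadjusted.** Chi-square or Fisher's exact test for categorical data, and "Proportion and relative risk (95% CI) will be presented for primary and secondary outcomes".
- **Adjusted.** "Multivariable logistic regression models will be created to control for potential confounders". The sentence does not say which outcomes are modelled, which covariates enter, or how many.
- **By race.** Under exploratory analyses, primary and secondary outcomes are to be analysed as Black versus non-Black, and an interaction of race is to be explored for counselling and follow-up.

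Fisher's exact test is the only provision for small counts, and it serves the unadjusted comparison. Nothing says what happens to a logistic model when a cell is empty or events are few.

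The Background reports that among women in the text-based monitoring programme "only 4% were counseled on CVD risk at their postpartum visits based on chart review". The same sentence gives 21% for counselling on primary care follow-up, and the Accrual section uses 21% as its usual-care rate. The sample size rests on the primary outcome alone.

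**The concern.** The trial is sized for an outcome expected in 21% of control patients, but the same analysis sentences reach an outcome expected in 4%. Ordinary maximum-likelihood logistic regression is biased away from the null when one arm has only a handful of events, and more so as covariates are added. When an arm-by-race cell has no events, the interaction estimate is infinite.

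The list of candidate covariates is long. The Procedures section plans to abstract demographics, medical and obstetric history, ten laboratory tests and three provider characteristics. Without a stated rule, the analyst would choose covariates and a rescue method after seeing an unstable odds ratio or an empty cell. Any bias in the adjusted odds ratio would favour the intervention, on an endpoint named in the opening hypothesis.

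**Working it through.** **1. The plan's own sample size.** Inputs: the Accrual section takes the primary-outcome rate as 21% in the control arm and 40% in the nudge arm, allows for 20% non-attendance, and states "A sample size of 222 patients (randomized 1:1) would provide 80% power to detect this difference". The Analysis Plan sets a two-sided alpha of 0.05.

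With unpooled variance, n per arm = (0.21×0.79 + 0.40×0.60) × (1.960 + 0.842)² / 0.19² = 0.4059 × 7.849 / 0.0361 = 88.3. Allowing for non-attendance, 88.3 / 0.80 = 110.3, rounded up to 111 per arm, or 222. The stated figure is reproduced.

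**2. Expected control events for CVD-risk documentation.** Attenders per arm: 111 × 0.80 = 88.8. Events: 88.8 × 0.04 = 3.55. The count is the same if all 111 are analysed and non-attenders count as not counselled. Applying 4% to all 111 gives 4.44. The primary outcome has 88.8 × 0.21 = 18.6 control events.

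**3. No control events at all.** 0.96^89 = 2.6%. The relative risk is therefore computable in about 97% of trials.

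**4. Race interaction.** The documents give no Black share, so 30 to 50% is assumed. The chance that at least one control race stratum has no event is 1 − (1 − 0.96^(89b)) × (1 − 0.96^(89(1−b))), where b is the Black share:

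| Black share | P(no event, Black) | P(no event, non-Black) | P(at least one empty) |
|---|---|---|---|
| 30% | 0.336 | 0.079 | 39% |
| 40% | 0.234 | 0.113 | 32% |
| 50% | 0.163 | 0.163 | 30% |

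Adding the two nudge-arm strata changes little if the nudge works. At a nudge rate of 15% the figures are 40% (30% Black) and 30% (50% Black); at 10% they are 43% and 31%. With 4% in both arms they are 1 − 0.612² = 63% and 1 − 0.701² = 51%. For the primary outcome, the chance of an empty control stratum is at most 1.5%, even at a Black share of 20 or 80%.

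**5. Adjusted odds ratio.** Simulation with 2,000 trials per setting, 89 per arm, control rate 4%, and either no covariates or five or eight. Nudge rate, covariate number and covariate strength are assumptions. Entries are the geometric mean of finite estimates against the true odds ratio (the true value shifts slightly with the covariates):

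| Nudge rate | No covariates | Five, ordinary | Five, Firth | Eight, ordinary | Eight, Firth |
|---|---|---|---|---|---|
| 4% (no effect) | 1.00 v 1.00 | 0.97 v 1.00 | 0.98 | 0.98 v 1.00 | 1.00 |
| 10% | 2.86 v 2.67 (+7%) | 2.92 v 2.70 (+8%) | 2.67 | 3.19 v 2.72 (+17%) | 2.71 |
| 15% | 4.61 v 4.24 (+9%) | 4.95 v 4.33 (+14%) | 4.35 | 5.21 v 4.40 (+18%) | 4.28 |
| 25% | 8.77 v 8.00 (+10%) | 10.07 v 8.35 (+21%) | 8.58 | 10.91 v 8.57 (+27%) | 8.49 |
| 40% | 17.92 v 16.00 (+12%) | 20.73 v 17.20 (+21%) | 17.07 | 23.84 v 17.95 (+33%) | 18.14 |

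Six covariates unrelated to outcome gave +9 to +17% at nudge rates of 10 to 25%. Firth's fit stays within about 3% of the truth throughout.

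**6. Bias against noise.** At 4% versus 15%, the crude log odds ratio has standard error √(1/3.56 + 1/85.44 + 1/13.35 + 1/75.65) = 0.62. The five-covariate bias is ln(4.95/4.33) = 0.13, about a fifth of that.

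**7. Unadjusted precision in the same case.** The relative risk is 0.15/0.04 = 3.75. Its 95% interval factor is exp(1.96 × √(1/3.56 − 1/89 + 1/13.35 − 1/89)) = 3.10, giving 1.2 to 11.6. The risk difference is 11 points, ± 1.96 × √(0.04×0.96/89 + 0.15×0.85/89) = 8.5, giving 2.5 to 19.5.

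**The case against.** The strongest reply is that the main inference is already sound. In a randomised trial the unadjusted comparison needs no covariates, and Fisher's exact test with proportions and a relative risk covers it. The logistic sentence never names this outcome, the race analysis is labelled exploratory, and the Abstract calls the trial a pilot. All of this stands, and it limits the point to supplementary analyses of one secondary endpoint.

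The 4% may also not hold. Providers can have patients in both arms, so prompts could raise control counselling. If the control rate doubled to 8%, expected events would be 88.8 × 0.08 = 7.1, and the chance of an empty control stratum would fall to 1 − (1 − 0.92^44.5)² = 5% at 50% Black, or 11% at 30%. The plan, however, takes the companion 21% as its usual-care rate, so 4% is the consistent planning value.

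Three stronger readings are tempting and not supported:

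- **The adjusted result will overstate the effect.** It does so on average only if the nudge works. With no effect there is no inflation, so the bias does not create an effect. Some 7 to 12% arises without any covariates.
- **The model will usually fail.** With five or eight covariates, 2 to 4% of fits were not finite when the nudge worked and 16 to 22% when it did not. These rates depend on covariate prevalence and can be much higher with uncommon covariates, but most such failures are in a covariate's coefficient and leave the treatment odds ratio finite.
- **The relative risk is invalid.** Its wide interval is honest imprecision, not an error.

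**Conclusion.** The gap is real but minor. The Analysis Plan expressly takes CVD-risk documentation into a race analysis, and on a natural reading into covariate-adjusted logistic models, with about 3.6 control events and no method suited to that count.

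The race interaction is the more serious part, because in roughly a third of trials there would be no finite logistic estimate to report. The inflation of the adjusted odds ratio is secondary. It is conditional on an effect, and a single trial's result would be dominated by sampling error.

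The event count rests on the historical 4% and the planned 20% non-attendance. The inflation and non-estimability figures also rest on assumed nudge rates of 10 to 40%, an assumed Black share, and assumed covariates. The primary outcome is not affected, and nothing here calls the unadjusted analyses into question.

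**What to change.** Add to the Analysis Plan, for documentation of CVD risk only:

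1. The unadjusted comparison (Fisher's exact test, proportions, relative risk with 95% interval) is the main result.
2. Any adjusted or race-interaction model is fitted by Firth penalised logistic regression with profile-likelihood confidence intervals, using a small set of baseline covariates named before the data are seen.

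A risk difference with a score-based interval (Miettinen-Nurminen or Newcombe) would help readers judge absolute benefit. It is an optional addition, not a correction. Ordinary models can stay for the primary outcome and for visit attendance.

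The cost is a sentence or two of text and standard software, with no change to sample size or data collection. The adjusted odds ratio will come out slightly smaller, and fewer covariates can be used for this endpoint. Firth's method makes the race interaction finite; it does not make it precise, so that result should still be read as exploratory.
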